1.3.3 Clinical Pharmacokinetics and Pharmacodynamics

In Phase 1 clinical trials, Lymphoseek showed rapid injection site clearance (approximately 2 to 3 hours). Absolute uptake in the primary sentinel lymph node was dose-related for Lymphoseek, although relative nodal uptake (%ID_{SN}) overall was independent of dose and ranged from 0.05%ID_{SN} to 1.81%ID_{SN}.

In a Phase 2 trial, Lymphoseek was highly effective in identifying tumor-draining lymph nodes (i.e., overall, a “hot spot” from Lymphoseek was identified in 93.0% of patients for whom preoperative lymphoscintigraphy was performed, and the per-patient intraoperative localization rate was 96.2%). Diagnostic performance of in vivo Lymphoseek findings relative to pathology assessment of tumor tissue indicated a high per tissue sensitivity estimate (overall, 92.0%). The overall false negative rate (FNR) for pathology was 8.0%, supporting the accuracy of Lymphoseek in identifying lymph nodes with a high potential for containing tumor metastases in the lymphatics draining the tumor bed.

1.3.4 Clinical Efficacy

Clinical efficacy was evaluated in two pivotal Phase 3 clinical trials in subjects with breast cancer and melanoma, comparing lymph node detection of Lymphoseek and vital blue dye (VBD). Lymphoseek demonstrated a statistically significant concordance rate with VBD (meta-analysis concordance rate = 99.99%).

The detection concordance between Lymphoseek and VBD was similar among subjects with melanoma and subjects with breast cancer (meta-analysis concordance rate = 99.99% for both populations). Lymphoseek also demonstrated a higher sensitivity for detecting tumor-positive (as confirmed by pathology) lymph nodes, corresponding to a decreased FNR when compared with VBD on a per node basis. The corresponding sensitivity rate in detection of lymph nodes most likely to be positive for tumor cells for Lymphoseek was 99.99%, compared with 78.02% for VBD. The FNR for VBD (21.98%) was higher than the FNR for Lymphoseek (0.01%). These findings suggest that, when VBD is used as the imaging agent, there is an increased risk of missing the detection of tumor-involved lymph nodes and incorrectly staging cancer patients. The Lymphoseek-only findings (pathology-positive nodes that were hot/not blue) suggest that Lymphoseek was markedly more effective in identifying lymph nodes that harbored disease than was VBD.

A third pivotal Phase 3 clinical trial was conducted in subjects with oral cavity or cutaneous SCC. Subjects received an injection of Lymphoseek prior to surgery for excision of the primary tumor and Lymphoseek-guided sentinel lymph node (SLN) dissection followed by planned elective neck dissection. All excised lymph nodes (Lymphoseek-identified SLNs as well as non-SLNs) underwent histopathologic evaluation for presence of metastatic disease. The primary endpoint in this trial was the Lymphoseek FNR (subjects with pathology-positive lymph node(s) not identified by Lymphoseek). Thirty-nine subjects had at least one pathology-positive lymph node, and Lymphoseek detected nodes with positive pathology in all but one patient. The FNR in this trial was 2.56%.

1.3.5 Clinical Safety

Well over 180,000 patients in clinical trials and US commercial use for ILM (intraoperative lymphatic mapping) with SLNB have been exposed to Lymphoseek, and there have been no safety signals, no deaths due to drug, and no SAEs (Serious Adverse Events) due to Lymphoseek. There are no known drug interactions leading to contraindications with the use of Lymphoseek. Post marketing reports have shown less than 0.12% of subjects experiencing adverse events, with the most common one being lack of node localization.

2 STUDY OBJECTIVES

2.1 Primary Objective(s)

- Determine the safety and tolerability of escalating doses of Tc 99m tilmanocept

2.2 Secondary Objective(s)

- Determine the localization of Tc 99m tilmanocept by SPECT (single photon emission computed tomography) imaging in subjects with active RA and asymptomatic controls and concordance of localization with clinical symptomology.
- Comparison of localization intensity between the dose groups of Tc 99m tilmanocept by SPECT imaging for optimal dose selection and determination of optimal imaging time.
- To estimate the pharmacokinetics (PK) and dosimetry of Tc 99m tilmanocept in subjects with and without active RA.

3 OVERVIEW OF METHODOLOGY AND DESIGN

3.1 Overall Study Design

Prospective, open-label, multicenter, dose escalation, and safety with PK and dosimetry study of injected Tc 99m tilmanocept in the detection of and assessment of localization to skeletal joints in subjects with and without active RA by SPECT imaging. Subjects will receive IV administration at one of 3 mass doses: 50 µg, 200 µg, or 400 µg. Within each mass dose group, subjects will receive Tc 99m tilmanocept labeled with one of 3 radiolabel doses: 1 mCi, 5 mCi, or 10 mCi. All subjects will have a whole body planar SPECT scan. Subjects enrolled in Groups 1-9 will receive a whole body planar SPECT scan and planar of hands at two specified time points: 60 minutes ± 15 minutes, and 180 minutes ± 15 minutes followed by a 3D SPECT or SPECT/CT scan on areas of interest. Subjects enrolled in Groups 10-11 will have a whole body planar SPECT scan with pharmacokinetic and dosimetry tests performed at 4 specified time points post injection: 15 ± 5 minutes, 60 ± 15 minutes, 180 ± 15 minutes, and 18-20 hours. Subjects enrolled in Groups 10-11 will also receive a planar SPECT hands scan at 60 ± 15 minutes and 180 ± 15 minutes post-injection. PK blood sampling will be performed before injection (within 15 minutes), immediately following injection (within 5 minutes), and at each scanning timepoint. Dosimetry tests will be performed at each scanning timepoint. PK of urine will be assessed through counts of the bladder wall obtained from cumulative quantitative planar imaging from radiation dosimetry. The proposed study includes 3 visits: A screening visit for initial determination of eligibility and evaluation of clinical status (Visit 1), a baseline: Day 1 (Visit 2) on the day of tilmanocept administration and imaging, and a safety follow-up (Visit 3).

The Schedule of Events ([Appendix 1](#)) contains a list of all study procedures and time points. Study activities are described in detail in [Section 7](#).

3.2 Justification for Study Design and Population

This study is designed to evaluate the safety and tolerability of escalating doses of Tc 99m tilmanocept. Whole body planar as well as a planar scan of the hands using a SPECT camera will also be combined with 3D SPECT or SPECT/CT imaging to provide greater resolution of areas of Tc 99m tilmanocept localization. Additionally, the PK and dosimetry of the MTD of Tc 99m tilmanocept will be evaluated in twelve subjects from Groups 10 and 11. Planar gamma camera imaging will be used to assess dosimetry.

This study is designed to evaluate the use of Tc 99m tilmanocept as an imaging agent in subjects with known active rheumatoid arthritis by evaluating the localization in inflamed joints.

No clinical trials have been conducted to evaluate IV administration of Tc 99m tilmanocept performance in subjects with rheumatoid arthritis. The rationale for evaluating Tc 99m tilmanocept in this subject population is discussed in [Section 1.1](#) and [Section 1.2](#).

3.3 Protocol Adherence

Strict adherence to all specifications outlined in this protocol is required for all aspects of the study conduct; the investigator may not modify or alter the procedures described in this protocol. If protocol modifications are necessary, all alterations that are not solely of an administrative nature require a formal protocol amendment for the involvement of Institutional Review Board(s) (IRB(s)).

If an investigator has deviated from the protocol in order to eliminate an immediate hazard to subjects or for other inevitable medical reasons, the investigator shall document all such deviations, including the reasons thereof, and submit the document to the sponsor and the IRB as applicable.

3.4 Study Duration

Subjects will be “on study” for up to 53 days depending on the duration of the screening window (up to 45 days) and Group assignment.

4 STUDY POPULATION

4.1 Eligibility

Subjects who fulfill all respective inclusion and none of the exclusion criteria will be eligible for enrollment into the study. All inclusion/exclusion criteria must be verified before a subject may be considered eligible for administration of Tc 99m tilmanocept and imaging (Day 1 procedures). A subject will be considered enrolled in the study on the morning of study day 1 when they arrive at the study site. Written, dated (with time noted) informed consent will be obtained from all subjects. A subject who withdraws consent prior to arrival at the study site on day 1 will be considered a screen failure.

4.1.1 Inclusion Criteria

ALL SUBJECTS:

1. The subject has provided written informed consent with HIPAA (Health Information Portability and Accountability Act) authorization before the initiation of any study-related procedures.
2. Has a negative urine drug screening for illicit or unprescribed drugs suggestive of drug abuse as determined by the investigator.
3. All subjects shall be ≥ 18 years of age at the time of consent.

CONTROL SUBJECTS:

4. The subject is deemed to be clinically free of any inflammatory disease (s) and has not experienced joint pain for at least 4 weeks prior to the consent date.

ACTIVE RHEUMATOID ARTHRITIS SUBJECTS:

4. The subject has moderate to severe RA as determined by the 2010 ACR/EULAR (score of $\geq 6/10$) that includes an affected hand and at least one large jointing (elbow, knee or shoulder).
5. The subject has a DAS28 of ≥ 3.2 (includes the Erythrocyte Sedimentation Rate [ESR] test and Visual Analog Scale [VAS]).
6. If the subject is receiving methotrexate, they have been at a stable dose for > 4 weeks prior to the Baseline Visit 2 (Day 1).
7. If the subject is receiving biologic therapy, they have been at a stable dose > 8 weeks prior to the Baseline Visit 2 (Day 1).
8. If the subject is receiving NSAIDS (nonsteroidal anti-inflammatory drug) or oral corticosteroids, the dose has been at a stable dose for > 4 weeks prior to the Baseline Visit 2 (Day 1). The corticosteroid dose should be ≤ 10 mg/day of prednisone or an equivalent steroid dose.

4.1.2 Exclusion Criteria

Subjects who meet any of the following criteria will be excluded from the study.

1. The subject is pregnant or lactating.
2. The subject size or weight is not compatible with imaging per the investigator.
3. The subject has had or is currently receiving radiation therapy or chemotherapy for a condition other than rheumatoid arthritis.
4. The subject has renal insufficiency as demonstrated by serum creatinine clearance of < 60 mL/min.
5. The subject has hepatic insufficiency as demonstrated by ALT (alanine aminotransferase [SGPT]) or AST (aspartate aminotransferase [SGOT]) greater than two times the upper limit of normal.
6. The subject has a chronic or persistent infection or has any condition that would, in the opinion of the examining physician, preclude their participation.
7. The subject has a known allergy to or has had an adverse reaction to dextran exposure.
8. The subject has received an investigational product within 30 days prior to the Tc 99m tilmanocept administration.
9. The subject has received any radiopharmaceutical within 7 days prior to the administration of Tc 99m tilmanocept.

4.2 Recruitment

Subjects will be recruited from rheumatology practices in accordance with the inclusion and exclusion criteria listed above. Potentially suitable subjects will be asked by their treating physician about their willingness to participate in this study. Healthy, “RA-free” subjects (controls) will be recruited via IRB approved advertisements and clinically assessed for the “absence” of painful and/or swollen joints.

4.3 Withdrawal

In accordance with the Declaration of Helsinki, each subject is free to withdraw from the study at any time and without providing a reason.

A subject who withdraws consent prior to arrival at the study site on Day 1 will be considered a screen failure.

Should a subject withdraw after administration of the investigational product, all efforts will be made to complete and report the observations up to the time of withdrawal as thoroughly as possible. An explanation should be given of why the subject is withdrawing or being withdrawn from the study.

The investigator may withdraw a subject from the study at any time at the discretion of the investigator for any of the following reasons:

- A protocol violation occurs
- A serious or intolerable AE occurs
- A clinically significant change in a laboratory parameter occurs
- At the investigator's/sponsor's discretion as long as it is in the best interest of the subject
- The sponsor or investigator terminates the study
- The subject requests to be discontinued from the study

4.4 Replacement

Subjects will be replaced under the following conditions:

- Subjects who did not receive study drug administration or did not proceed to imaging

4.5 Subject Identification

After the subject provides written informed consent, the site will assign the subject a 7-digit subject number. Subject numbers are to be assigned in a sequential manner using the following format:

Digits 1 to 2: Study number "21"

Digits 3 to 4: Site number (e.g., "01")

Digits 5 to 7: Sequential subject number (e.g., "001", "002", "003")

For example, the first subject consented at Site 01 is subject number "21-01-001."

Subjects will maintain the same number given at screening for the entire study. If a subject is a screen failure, the number will not be used for any other subject.

5 INVESTIGATIONAL PRODUCT

5.1 Identification of Investigational Product

Technetium Tc 99m tilmanocept is a radiopharmaceutical that binds to mannose binding receptors (CD206) that reside on the surfaces of dendritic cells and macrophages.

5.2 Investigational Product Dosage and Administration

Subjects will receive the administration of Tc 99m tilmanocept through an intravenous (IV) route of administration. For the 50 and 200 µg doses a single syringe will be used and injected as a slow push into the Y-port. For the 400 µg dose 2 syringes will be used and injected sequentially as a slow push into the Y-port. At the completion of the injection(s), a 10 cc sterile normal saline flush will be administered. Injection volume will be between 0.5 - 4.0 ml in sterile normal saline based on the mass dose group assignment. The preferred site of IV placement will be the left or right antecubital vein unless both elbows are primary sites for RA imaging, and then the site for IV placement will be between the elbow and the wrist.

Tc 99m tilmanocept will be received by subjects through IV administration at one of 3 mass doses: 50 µg, 200 µg, or 400 µg. Within each mass dose group, subjects will receive Tc 99m tilmanocept labeled to one of 3 radiolabel doses: 1 mCi, 5 mCi, or 10 mCi (see Table 1).

Table 1. Dose Escalation Matrix

	Tilmanocept Mass Dose		
Specific Radioactivity Tc 99m	50 µg	200 µg	400 µg
10 mCi	Group 1 n = 3 RA	Group 2 n = 3 RA	Group 3 n = 3 RA
5 mCi	Group 4 n = 3 RA	Group 5 n = 3 RA	Group 6 n = 3 RA
1 mCi	Group 7 n = 3 RA	Group 8 n = 3 RA	Group 9 n = 3 RA

***Group 10 will consist of 6 HC (3 female subjects and 3 male subjects) and Group 11 will consist of 6 subjects (3 female subjects and 3 male subjects) with active RA. Subjects in Groups 10 and 11 will be enrolled in parallel and will be dosed at the MTDs determined from Groups 1-9.**

The final administered dose for groups will be ± 20% of the tilmanocept mass dose and radiolabel mCi dose assignment.

5.3 Treatment Assignment

In this open-label, non-randomized, multicenter, dose-escalation safety study all subjects will receive IV administration at one of 3 tilmanocept mass doses: 50 µg, 200 µg, or 400 µg. Within each mass dose group, subjects will receive tilmanocept labeled to one of 3 radiolabel Tc 99m doses: 1 mCi, 5 mCi, or 10 mCi.

Group 1 will be the starting dose group. Three subjects will be enrolled into Group 1. If none of the 3 subjects experiences pharmacologic activity or an ADR, 3 subjects will be enrolled in Group 2. However, if one of the first three subjects experiences a pharmacologic activity or an ADR, three more subjects will be treated at the same dose level. If 2 out of 3 or 3 out of 6 subjects experiences a pharmacologic activity or an ADR in Group 1 the MTD cannot be determined. If no additional pharmacologic activity or ADRs are observed in the expanded group, the dose escalation will continue. If one additional pharmacologic activity or ADR is observed, the current dose will be deemed the maximum tolerated dose (MTD). If more than one additional pharmacologic activity or ADR is observed in the expanded group, the previous dose will be deemed the MTD. Dose escalation will continue until the MTD is found or until Group 9 is reached with only one ADR or without any ADRs. If no ADRs are experienced from Groups 1-9, then the MTD will be highest tilmanocept mass dose radiolabeled at the highest level (400 µg/10 mCi).

Group 10 will consist of 6 HC subjects and Group 11 will consist of 6 subjects with active RA. Subjects enrolled in Groups 10 and 11 will be dosed at the dose level that is established as the MTD from Groups 1 through 9. The maximum tolerated dose is defined as the dose below where >33% of subjects experienced an ADR.

NOTE: Adverse Drug Reaction

An Adverse drug reaction (ADR) includes all noxious and unintended responses to a medicinal product related to any dose or dose regimen. The phrase “responses to a medicinal product” means that a casual relationship between a medicinal product and an adverse event is at least a reasonable possibility, i.e. the relationship cannot be ruled out.

In this multi-center trial, doses will be serially assigned in an open label fashion in accordance with [Table 1](#). Investigators who have identified a subject for participation will receive the dose assignment from the sponsor and request that dose from the supporting Cardinal Health pharmacy.

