9.4 Sample Size Justification

The dose escalation portion of this study is a modified 3+3 design with no dose de-escalation. The sequential cohort enrollment characteristics of this design do not allow a fixed computation of sample size. The parameters of the design that can be calculated are shown in [Table 4](#). Based on an assumed vector of probabilities of any pharmacologic activity or an ADR for a subject, the probability of each dose being the MTD is shown in the table. The average sample size of the dose escalation phase of the study is $n=26.3$ patients for the assumed vector of probabilities of any pharmacologic activity or an ADR.

Table 4. Design Characteristics for the Study Design

Dose Group	1	2	3	4	5	6	7	8	9	Total
Assumed Probability of any pharmacologic activity or a ADR for a subject	.01	.02	.05	.08	.10	.13	.16	.19	.22	---
Probability of the Dose Being the MTD	.002	.012	.039	.071	.103	.136	.152	.148	.065	---
Average Sample Size for Each Dose and Total	3.1	3.2	3.4	3.5	3.3	3.2	2.8	2.2	1.6	26.3

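### Section 5.3: if Group 4 or Group 7 fails, the MTD becomes a dose with 8 times the mass and 2 or 5 times the activity of the dose that failed

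*Combined protocol and SAP*

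**What the plan says.** Table 1 (section 5.2) numbers nine groups along rows of falling activity: Groups 1-3 are 50, 200 and 400 µg at 10 mCi, Groups 4-6 the same masses at 5 mCi, and Groups 7-9 the same masses at 1 mCi. Section 5.3 starts at Group 1, goes to Group 2, assigns doses serially by Table 1, and ends at Group 9.

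An event is pharmacologic activity or an ADR. After one event in the first 3 subjects, 3 more are treated. No further event continues escalation; one further event makes the current dose the MTD; for more than one further event, "the previous dose will be deemed the MTD". For Group 1 alone, failure has a separate outcome: after 2 of 3 or "3 out of 6 subjects experiences a pharmacologic activity or an ADR in Group 1 the MTD cannot be determined".

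Two other sentences in 5.3 bear on the ordering. The definition reads "The maximum tolerated dose is defined as the dose below where >33% of subjects experienced an ADR". If Groups 1-9 show no ADR, "the MTD will be highest tilmanocept mass dose radiolabeled at the highest level", given there as 400 µg/10 mCi, which is Group 3. Groups 10 and 11 (6 healthy controls, 6 subjects with RA) "will be dosed at the dose level that is established as the MTD".

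Table 4 (section 9.4) has a row headed "Assumed Probability of any pharmacologic activity or a ADR for a subject" that rises from .01 in Group 1 to .22 in Group 9.

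**The concern.** A fallback to the previous dose is sound when the previous dose is the smaller one. That holds for Groups 2, 3, 5, 6, 8 and 9, whose predecessor has lower mass at the same activity. It does not hold for Groups 4 and 7, where the predecessor is higher in both mass and activity. The no-ADR rule ranks doses by amount, so 5.3 itself treats Group 3, not Group 9, as the top of the matrix. The definition says the MTD lies below the failing dose but does not say in which ordering.

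At stake is the dose for 12 subjects, half of them healthy. After a failure at 50 µg/5 mCi the text sends them to the largest dose in the study. Whether that dose is riskier depends on what drives risk. Section 8.6.1.4 expects no adverse events from the radioactive dose, and the rat findings in section 1.3.2 vary with mass (at tens of times the human dose), so risk that follows mass is plausible. Table 4 assumes instead that risk rises with group number.

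**Working it through.** **1. What the previous dose is (Table 1).**

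| Group that fails | Previous group | Mass ratio | Activity ratio |
|---|---|---|---|
| 4: 50 µg/5 mCi | 3: 400 µg/10 mCi | 400/50 = 8 | 10/5 = 2 |
| 7: 50 µg/1 mCi | 6: 400 µg/5 mCi | 400/50 = 8 | 5/1 = 5 |

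**2. Reproducing Table 4.** Inputs: p = .01, .02, .05, .08, .10, .13, .16, .19, .22. For each group let a = (1−p)³, c = 3p(1−p)², d = 1−a−c. Then:
- escalate: a + ca
- current group is the MTD (2 of 6): c²
- previous group is the MTD: d (2 or 3 of the first 3) plus cd (3 or more of 6)
- probability R of reaching a group: the product of (a + ca) over earlier groups

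Result: .002 .012 .039 .071 .103 .136 .153 .148 .065. Table 4 has .152 for Group 7 and is otherwise identical. The match requires the previous dose to mean group number minus 1, and 2 or 3 of the first 3 to go to that group. The sample-size row matches less closely: 26.5 against 26.3 in total, with Group 9 at 1.71 against 1.6.

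**3. Probability that Group 4 or 7 fails, Table 4's risks.**

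| | R | c | d | 3+ of 6: R·c·d | 2+ of first 3: R·d |
|---|---|---|---|---|---|
| Group 4 | .9679 | .2031 | .0182 | .0036 | .0176 |
| Group 7 | .7008 | .3387 | .0686 | .0163 | .0481 |
| Sum | | | | .0199 | .0657 |

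The written step gives 0.020; both branches give .0199 + .0657 = 0.086 (rounded). In this scenario the named group has the lower assumed risk: .05 against .08, and .13 against .16.

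**4. Same probability if risk follows mass only.** The documents give no such rates. The rates below for 50/200/400 µg are assumptions, repeated in each row of Table 1.

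| Rates | Written step | Both branches |
|---|---|---|
| .01/.02/.05 | 0.002% | 0.06% |
| .02/.05/.10 | 0.011% | 0.2% |
| .05/.10/.20 | 0.10% | 0.8% |
| .10/.20/.30 | 0.28% | 1.5% |

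Here the named dose is the riskier one, for example .20 against .05 in the third line.

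**5. Outcomes where all nine groups pass (Table 4's risks, all events counted as ADRs).** All pass: product of (a + ca) = .2700. No event at all: product of (1−p)³ = .0438. Pass with at least one event: .2700 − .0438 = .226 (unrounded .2263), for which 5.3 names no MTD. The no-ADR rule sends .044 to Group 3, so its total should be .039 + .044 = .083. Table 4's MTD row leaves this out.

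**6. MTD row under the rules proposed below.** Group 3: own 2 of 6 (.0182) + all pass (.2700) = .288. Group 6: own 2 of 6 only = .072. Not determined: .0855 + .0003 (Group 1 fails) = .086. Other groups are unchanged. Check: .002 + .012 + .288 + .071 + .103 + .072 + .153 + .148 + .065 + .086 = 1.000.

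**The case against.** The strongest reply is that sequence order is settled for the failure branch. Doses are serially assigned, Table 4 was computed that way, and if below means earlier in sequence, the definition and the fallback agree. The fallback and the no-ADR rule also act on mutually exclusive outcomes. This stands against a reading that a reader might adopt, namely that 5.3 contradicts itself because both orderings cannot govern: no trial path triggers both. It does not make it sound to name a dose higher in both components than the one that failed.

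Three other stronger readings are not supported:
- **That 8.6% is a probability of harm.** It comes from Table 4's risks, under which the named group is the safer one. Where the named dose is riskier, the probabilities are those in step 4. Group 3 or 6 would also have passed in its own right, at 0 of 3 or 1 of 6.
- **That nothing covers 2 or 3 events in the first 3 outside Group 1.** For ADRs, 2 of 3 is 67%, so the definition sentence implies the outcome. Only pharmacologic activity without an ADR is left uncovered.
- **That the 33% threshold conflicts with making a 2-of-6 group the MTD.** This is rounding of one third, and the explicit 2-of-6 step settles it.

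Two criticisms of the remedy have some force. Leaving the MTD undetermined is a cautious choice, not the only defensible one. And sequence escalation remains: a 2-of-6 result in Group 4 or 7 (.0399 + .0804 = 0.120 under Table 4's risks) still makes a 50 µg dose the MTD after 400 µg passed. That errs towards a lower dose, so it is a different matter.

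**Conclusion.** The point holds as a defect in the dose-setting rule, not as a demonstrated hazard. As written and as computed in Table 4, failure in Group 4 or 7 assigns Groups 10-11 a dose 8 times higher in mass and 2 or 5 times higher in activity than the one that failed, while the no-ADR rule ranks doses by amount.

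The probability rests on the assumed risks: 0.020 (written step) or 0.086 (both branches) under Table 4's vector, and at most 0.28% or 1.5% under the mass-only rates tried. Two related gaps are larger or of similar size under Table 4's vector with every event counted as an ADR: no MTD is named in 0.226 of trials, and Table 4 gives Group 3 .039 where the written rules give .083. Healthy subjects receive the resulting dose and the repair is cheap, so 5.3 should be amended.

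**What to change.** In section 5.3:
1. State that in Groups 2-9, 2 or more events in the first 3, or 3 or more in 6, stops escalation.
2. Make the previous group the MTD only if it is no higher in mass and no higher in activity than the group that failed. For Groups 4 and 7 the MTD is then not determined, as already written for Group 1, and Groups 10-11 are not dosed until the sponsor sets their dose after safety review.
3. Apply the 400 µg/10 mCi rule whenever all nine groups pass, not only when no ADR occurs. Group 3 has itself passed in every such case.
4. Recompute Table 4's MTD row under these rules; step 6 of the working gives the expected values.

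As wording only, replace the 33% threshold by more than 2 of 6.

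The cost is a few sentences by amendment and one recomputed row, with no extra subjects. The downside is that if Group 4 or 7 fails, the PK and dosimetry work in Groups 10-11 waits for a dose decision although Group 3 or 6 had itself passed.

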 - Assessment of adverse events

	
Post-Tc 99m Tilmanocept Injection Procedures and Follow-Up Visit (Visit 3):
 
 • 18-20 Hours Post Injection: 
 ○ Whole body planar imaging ○ PK blood sampling ○ Vital Signs ○ ECG ○ Physical Exam, including body weight ○ Clinical labs and urinalysis ○ Concomitant medication review ○ Assessment of Adverse Events 	

Planned study dates
	
Start of study recruitment / August 2016
	
End of Recruitment/July 2018 End of Study/September 2018

Planned number of study centers
	
Approximately 1-3 centers in the United States
	

Number of subjects
	
Up to 48 evaluable subjects may be enrolled. The dose escalation portion of this study is a modified 3+3 design with no dose de-escalation. The sequential cohort enrollment characteristics of this design do not allow a fixed computation of sample size. The parameters of the design that can be calculated are shown in Table 4. Based on an assumed vector of probabilities of no subjects experiencing pharmacologic activity or an Adverse Drug Reaction (ADR) in each dose group, the average sample size of the dose escalation phase of the study is n=26.3 patients and the probability that dose group 7 will be selected as the MTD (maximum tolerated dose) is 0.152.
	

Primary endpoint
	
Proportion of subjects not experiencing pharmacologic activity or ADR in each dose group.
	

Secondary endpoints
	
The secondary endpoints for this study are:
 
 • Per subject localization rate of Tc 99m tilmanocept by SPECT imaging • Per joint location clinically RA-identified joint localization rate of Tc 99m tilmanocept by SPECT imaging • Concordance of Tc 99m localization with anatomical areas of active RA defined by clinical symptomology. • Localization intensity for each clinically RA-defined joint (as determined by quantitative SPECT gamma counts) 	

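### Section 5.3 names no MTD when all nine groups pass with an isolated ADR (probability up to 0.226 under Table 4's assumptions), and Table 4 leaves out the written fallback to Group 3

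*Combined protocol and SAP*

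**What the plan says.** Section 5.3 (Treatment Assignment) sets the escalation rules. A group with no event among three subjects passes. With one event, "three more subjects will be treated at the same dose level". No further event lets escalation continue, one further event makes the current dose the MTD, and more than one makes the previous dose the MTD. The event in these rules is pharmacologic activity or an ADR.

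Three later sentences speak of ADRs only:
- The end of escalation: "Dose escalation will continue until the MTD is found or until Group 9 is reached with only one ADR or without any ADRs".
- The fallback: "If no ADRs are experienced from Groups 1-9, then the MTD will be highest tilmanocept mass dose", at the highest radiolabel level. This is 400 µg/10 mCi, which Table 1 lists as Group 3.
- The general definition: "The maximum tolerated dose is defined as the dose below where >33% of subjects experienced an ADR".

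Subjects in Groups 10 and 11 "will be dosed at the dose level that is established as the MTD from Groups 1 through 9".

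Section 9.4, Table 4, gives a row headed "Assumed Probability of any pharmacologic activity or a ADR for a subject" and a row headed "Probability of the Dose Being the MTD". The synopsis, under the number of subjects, quotes one entry from the second: "the probability that dose group 7 will be selected as the MTD (maximum tolerated dose) is 0.152". Section 8.1.1 sets a ceiling of 36 subjects in Groups 1-9 and 48 overall.

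**The concern.** The stop sentence foresees that escalation may end at Group 9 with an ADR and no MTD found. The fallback that follows covers only the case of no ADR at all. Whether 'only one ADR' means one in Group 9 or one in the whole escalation, no dose is named. The general definition does not help, because a group that passes has 0/3 or 1/6 events, at most 16.7%, so no dose exceeds 33%.

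The MTD sets the dose of all 12 subjects who supply the PK and dosimetry data. A foreseen ending therefore leaves that dose unassigned.

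Table 4 has a related fault. If its MTD row describes only the stopping rules, it understates Group 3, which the written fallback also selects, and it hides how often no dose stops the escalation.

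**Working it through.** **Inputs.** Event probabilities p for Groups 1-9 from Table 4: .01, .02, .05, .08, .10, .13, .16, .19, .22. Rules from section 5.3. One assumption: two or more events among the first three subjects in Groups 2-9 make the previous dose the MTD. Section 5.3 spells this case out only for Group 1, but this reading reproduces Table 4.

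**Formulas for each group.**
- q0 = (1−p)³, q1 = 3p(1−p)², q2 = 1 − q0 − q1.
- Pass: q0 + q1·q0.
- Current dose is the MTD: q1².
- Previous dose is the MTD: q2 + q1·q2.
- Reach of a group: the product of the pass probabilities of all earlier groups.
- P(MTD = i) = reach(i)·current(i) + reach(i+1)·previous(i+1). Group 9 has the first term only.

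**Reproducing Table 4.**

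| Group | 1 | 2 | 3 | 4 | 5 | 6 | 7 | 8 | 9 | Sum |
|---|---|---|---|---|---|---|---|---|---|---|
| Computed | .0021 | .0115 | .0394 | .0715 | .1028 | .1360 | .1526 | .1483 | .0655 | .7297 |
| Printed | .002 | .012 | .039 | .071 | .103 | .136 | .152 | .148 | .065 | .728 |

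Every entry agrees within .001. The usual 3+3 variant, in which 2/6 selects the previous dose and a full pass is given to Group 9, yields .061 for Group 3 and .270 for Group 9, so it is not what was tabulated. The average sample size comes to 26.5 against the printed 26.3, a small difference that does not affect this point.

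**What is missing from the row.** The pass probabilities are .9988, .9954, .9734, .9369, .9061, .8529, .7934, .7302 and .6651; their product is 0.2700. A failure in Group 1, where the MTD cannot be determined, has probability 0.0003. Check: .7297 + .2700 + .0003 = 1. The row therefore gives the all-pass outcome to no dose.

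**Splitting the 0.2700.**
- No event in any of the 27 subjects: product of the q0 = 0.0438.
- At least one event: 0.2700 − 0.0438 = 0.226 (0.2263 before rounding the terms), made up of exactly one event (0.091) and two or more (0.135).

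**Group 3.** The stopping rules give .0182 + .0212 = .0394. Adding the fallback as written: .0394 + .0438 = .083. If the fallback covers every all-pass trial: .0394 + .2700 = .309.

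**Why 0.226 is an upper bound.** Table 4's vector counts pharmacologic activity or an ADR, while the fallback turns on ADRs only. If a share s of events are ADRs (assumed, equal in all groups), the all-pass outcome without an ADR is the product of q0·(1 + q1·(1−s)).

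| ADR share s | All pass, no ADR | Gap | Group 3, fallback as written |
|---|---|---|---|
| 1 | .044 | .226 | .083 |
| .75 | .072 | .198 | .112 |
| .50 | .115 | .155 | .155 |
| .25 | .179 | .091 | .218 |

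**Other event rates, every event an ADR.** The gap is not monotone in the rate.

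| Event probabilities | Gap |
|---|---|
| 1.5 × vector | 0.060 |
| Table 4 vector | 0.226 |
| 0.5 × vector | 0.468 |
| 0.25 × vector | 0.425 |
| 0.1 × vector | 0.235 |
| constant 3/553 | 0.133 |
| constant 0.12% | 0.032 |

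The figure 3/553 is the count of definitely related events in section 8.6.1.4; 0.12% is the post-marketing figure in section 1.3.5.

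**Ceiling.** Nine groups of six is 54. Under the same recursion, P(more than 36 subjects in Groups 1-9) = 0.028.

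**The case against.** The best reply is that the intended dose is plain. If all nine groups pass, Group 3 has passed, and no cell of Table 1 exceeds it in mass or activity. The written fallback already skips the last group in sequence to select it. This stands, and it makes the repair one of wording. The text still limits that fallback to the case of no ADR.

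A reader might go further and infer that Groups 10 and 11 could be given Group 9 (400 µg/1 mCi), with too little activity left at the 18-20 hour scan. The documents do not support this. The fallback and Table 1 point away from Group 9, and no minimum activity for that scan is stated. Nor would a dose that failed the rules be given, since every group has passed in this outcome. The primary endpoint is tabulated by dose group and does not depend on the MTD.

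Prior safety data suggest few events, in which case the existing fallback covers most trials: 0.863 at 3/553 and 0.968 at 0.12%. That is a fair limit on the size. However, the post-marketing routes listed were not intravenous, and section 5.3's definition of an ADR takes in any event whose relationship cannot be ruled out, which is wider than definitely related.

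Table 4 prints no total for its MTD row, no analysis uses the row, and 0.152 for Group 7 is right under the stopping rules. All true, but the row's heading claims the probability that each dose is the MTD, and for Group 3 that conflicts with section 5.3.

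One might also infer that the ceilings of 36 and 48 must rise to 54 and 66. They are enrolment limits, and a 0.028 chance of passing 36 does not justify that.

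**Conclusion.** The point holds and should be fixed. Section 5.3 foresees an ending for which it names no MTD and so leaves the dose of 12 subjects unassigned. Under Table 4's vector the probability is up to 0.226, and lower to the extent that events are pharmacologic activity only. Over the other rates tried it ranges from 0.032 to 0.468.

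Table 4's .039 for Group 3 is inconsistent with the written fallback and should be at least .083. The unreported no-stop outcome, 0.270, exceeds every printed entry.

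These figures assume independent subjects, Table 4's probabilities, and the previous-dose reading of two or more events among the first three in Groups 2-9, which is supported by the match to the printed row. The consequence is an unassigned dose and a misstated design property; the documents show neither a safety hazard nor a loss of dosimetry data.

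**What to change.** - **Section 5.3:** state that the MTD is 400 µg/10 mCi whenever all nine groups pass, with or without isolated events. Use pharmacologic activity or ADR in the stop, fallback and definition sentences, so that they match the stopping rules and Table 4.
- **Table 4:** set Group 3 to .309 and state that 0.270 of it is the outcome in which no dose stops escalation.
- **Synopsis:** reword the Group 7 sentence to match, since under the extended rule Group 3 is the most probable MTD (.309 against 0.152).
- **Minor:** say what happens if Groups 1-9 reach 36 subjects before escalation ends, and leave the ceilings as they are.

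The cost is a few sentences and one table entry with a note. No new procedures or subjects are needed.
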